2.11 Patient-reported outcomes

The impact of ligelizumab on the health-related quality of life (HRQoL) of participants with a food allergy will be assessed by the following measures based on age group and responder type:

- FAQLQ-CF: Food Allergy Quality of Life Questionnaire Child Form (completed by children aged 8-12)
- FAIM-CF: Food Allergy Independent Measure Child Form (completed by children aged 8-12)
- FAQLQ-TF: Food Allergy Quality of Life Questionnaire Teenager Form (completed by adolescents aged 13-17)
- FAIM-TF: Food Allergy Independent Measure Teenager Form (completed by adolescents aged 13-17)
- FAQLQ-AF: Food Allergy Quality of Life Questionnaire Adult Form (completed by adults aged 18-55)

- FAIM-AF: Food Allergy Independent Measure Adult Form (completed by adults aged 18-55)
- FAOLO-PF: Food Allergy Quality of Life Questionnaire Parental Form (completed by same parent/caregiver of children aged 0-12)
- FAQL-PB: Food Allergy Quality of Life Parental Burden Questionnaire (completed by same parent/caregiver of children aged 0-17)

Table 2-2 PROs based on participant's age

		•	•					
Age Group/ Respondent Type	Questionnaire	Day 1 Screening	Week 52 10 days Before OFC	Week 52 3 days After OFC	Week 104 10 days Before OFC	Week 104 3 days After OFC	Week 156 10 days Before OFC	Week 156 3 days After OFC
Children aged	FAQLQ-CF	X	Х	Χ	Х	Х	Χ	Х
12	FAIM-CF	X	Χ	Х	Х	Х	Х	Х
Teenagers aged	FAQLQ-TF	х	Х	Х	X	X	X	Х
13-17	FAIM-TF	х	Х	Х	X	X	X	Х
Adults aged 18+	FAQLQ-AF	x	X	Х	X	X	х	X
	FAIM-AF SF-36v2	X	X	X	X	X	X	Х
Parents/	FAQLQ-PF	x	Х	Х	X	X	х	х
Caregivers of Children aged 13-17	FAQL-PB	Х	X	X	Х	X	X	X
Parents/ Caregivers of Children aged 12	FAQL-PB	х		X		X		X

The Food Allergy Quality of Life Questionnaire (FAQLQ) is a self-reported instrument intended to assess the effect of food allergy on the participant's HRQoL (i.e., domains consist of risk of accidental exposure, emotional impact, allergen avoidance and dietary restrictions). The FAQLQ- Child Form (aged 8-12) (Flokstra-de Blok et al 2009a), FAQLQ-Teenager Form (aged 13-17) Flokstra-de Blok et al 2008) and FAOLO-Adult Form (>18 years of age) (Flokstra-de Blok et al 2009b), are self-administered, validated, food allergy-specific HRQoL questionnaires. The FAQLQ-parental form (FAQLQ-PF) is completed by parents of children aged 0-12 with food allergy (DunnGalvin et al 2008).

The number of items and domains varies by FAQLQ instrument administered. Each question is scored on a seven-point scale from 1 to 7 (i.e., from 'no' to 'maximal' impairment in HRQoL, respectively). The total score is the arithmetic average of all non-missing items. Domain scores are calculated similarly.

The Food Allergy Independent Measure (FAIM) reflects the participant's perceived food allergy severity and food allergy-related risk. The total score for the FAIM ranges from 1 to 7 (i.e., from 'limited' to 'the greatest' severity perception). If less than 80% of the items are complete, then the total score will not be calculated. Similarly, if less than 80% of the items within a domain are complete, then the domain score will not be calculated. (van der Velde et al 2010)

The Food Allergy Quality of Life-Parental Burden (FAQL-PB) Questionnaire is a self-administered, disease-specific instrument developed to measure the effect of pediatric food allergy on HRQoL among caregivers. The instrument includes 17 items investigating the effect of having a child with food allergy on family/social activities, school, meal preparation, health concerns and emotional issues, using a 7-point Likert scale (Cohen et al 2004).

The SF-36v2[®] Health Survey is a 36-item instrument for measuring health status and outcomes via participant self-report. It is designed for use in surveys of general and specific populations, health policy evaluations, and clinical practice and research. The SF-6Dv2 (Brazier et al 2020) will be derived from the SF-36v2 (Maruish 2011) for health economic evaluations. The SF-6Dv2 captures the impacts of food allergy on social activities and depression/nervousness.

All questionnaires will be completed in the language most familiar to the respondent. The same parent/caregiver should complete the assessments throughout the study.

The participant should be given sufficient instruction, space, time and privacy to complete the questionnaire during the Screening visit. The study coordinator should encourage the participants to complete all of the available questionnaires.

All participants will complete the PRO questions via a handheld electronic device (note: children aged 6-7 will NOT be completing any PRO measures). Participants will take the device home and should complete them 10 days before (pre) the OFC and 3 days after (post) the OFC at Week 52, 104 and 156. For analysis, will consider latest non-missing measurements. If the 'post-' measurement is missing, then the non-missing 'pre-' measurement will be used. If participants experience any difficulties with submission after completing the PROs, they should contact the study staff for assistance. Available training materials related to the administrative procedures of the questionnaires will be provided to the sites.

Participant refusal to complete study PROs is not a protocol deviation. The participant should be made aware that completed measures are not reviewed by the investigator/study personnel.

Scoring of PRO Instruments

The number of items and domains varies by FAQLQ instrument administered. Each question is scored on a 7-point scale (0-6 coded as 1-7 in analysis, with a higher level indicating greater impairment in HRQoL). The total score is the arithmetic average of all completed items. Domain scores are calculated similarly for each form as following:

FAQLQ-CF: Emotional impact (EI) (item no. 19-24), Allergen avoidance (AA) (item no. 4, 6-10, 15), Risk of accidental exposure (RAE) (item no. 11, 13, 14, 16, 17), Dietary restriction (DR) (item no. 1-3, 5, 12, 18)

FAQLQ-TF: Emotional impact (EI) (item no. 5, 12, 19-23), Allergen avoidance and dietary restrictions (AADR) (item no. 1-4, 6-10, 16), Risk of accidental exposure (RAE) (item no. 11, 13-15, 17, 18)

FAQLQ-AF: Emotional impact (EI) (item no. 5, 24-29), Allergen avoidance and dietary restrictions (AADR) (item no. 1-4, 6, 8-12, 20), Risk of Accidental Exposure (RAE) (item no. 7, 13-18, 21), Food allergy related health (FAH) (item no. 19, 22, 23)

CSR SAP Amendment 1

FAQLQ-PF: Emotional impact (EI) (item no. 2, 6, 7, 9-11, 23-28, 30), Food anxiety (FA) (item no. 1, 4, 5, 16, 17, 20, 21, 29), Social and dietary limitations (SDL) (item no. 3, 8, 12-15, 18, 19, 22).

If more than one item in any domain is missing, a domain score should not be calculated for that case. A total score can still be calculated if 20% or fewer of the items are missing.

The FAIM reflects the participant's perceived food allergy severity and food allergy-related risk (van der Velde, Flokstra-de Blok et al. 2010). Each question is scored on a 7-point scale (0-6 coded as 1-7 in analysis, with a greater score indicating a higher level of perceived risk or chance of adverse events occurring). The total score is the arithmetic average of all completed items. If less than 80% of the items within the score are complete, it will not be calculated. Questions 4 and 5 (effectively managing a reaction, receiving sufficient help from others) must be reverse coded.

A threshold of 0.45 points has been suggested and used as a minimal important difference (MID) to interpret clinical relevance (Dunn Galvin, Cullinane et al. 2010). For FAQLQ and FAIM forms, the 0.45 threshold will be used to interpret the clinical relevance of group-level differences and changes, in addition to within-patient changes.

The FAQL-PB is a self-administered, disease-specific instrument developed to measure the effect of pediatric food allergy on HRQoL for caregivers (Cohen, Noone et al. 2004). The instrument includes 17 items (assessing social, dietary and emotional impacts) on the impact of having a child with food allergy on the parents themselves using a 7-point Likert scale ranging from 0 (not limited/troubled) to 6 (extremely limited/troubled). The total score is the arithmetic average of all completed items.

The SF-36v2® Health Survey is a 36-item instrument that measures generic health-related quality of life. It is designed for use in surveys of general and specific populations, health policy evaluations and clinical practice and research. Two forms of this instrument are available and this study will use the one-week recall (acute) form. The SF-36v2 contains 8 scales and 2 component summary indices evaluating physical, social and emotional functioning in addition to general health perceptions and mental health. Responses to items allow for direct calculation of scale scores, while the physical component summary (PCS) and mental component summary (MCS) scores are computed from weighted scale scores. The SF-36v2 scale and composite scores can be converted to a T-score metric, allowing for norm-based scores derived from responses to a 2009 survey conducted by QualityMetric. For all scales and summary measures, higher scores indicate better health outcomes.

The SF-6Dv2 may be derived from the SF-36v2 for health economic evaluations (Brazier, Mulhern et al. 2020). The SF-6Dv2 captures the impact of diseases and conditions on social activities and depression/nervousness. The SF-6Dv2 questionnaire uses a standardized health state descriptive system consisting of 6 dimensions, including social limitations, which was deemed essential to cover in food allergy. All dimensions are expressed over 5 levels, except for pain, which uses 6 levels, allowing for the description of 18,750 different health states. Health states are described using a combination of 6 digits each expressing the level for a dimension. For example, state "111111" indicates perfect health and state "555655" indicates the worst possible health status. The resulting SF-6Dv2 index, scored from 0.0 (worst health state) to 1.0 (best health state), can be used in the assessment of the quality adjusted life years (QALYs) and the cost-effectiveness of various health care interventions.

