All questionnaires will be completed in the language most familiar to the respondent. The same parent/caregiver should complete the assessments throughout the study.

The participant should be given sufficient instruction, space, time and privacy to complete the questionnaire during the Screening visit. The study coordinator should encourage the participants to complete all of the available questionnaires.

All participants will complete the PRO questions via a handheld electronic device (note: children aged 6-7 will NOT be completing any PRO measures). Participants will take the device home and should complete them 10 days before the OFC and 3 days after the OFC at Week 52, 104 and 156. If participants experience any difficulties with submission after completing the PROs, they should contact the study staff for assistance. Available training materials related to the administrative procedures of the questionnaires will be provided to the sites.

Participant refusal to complete study PROs is not a protocol deviation. The participant should be made aware that completed measures are not reviewed by the investigator/study personnel.

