2.6 Analysis supporting secondary objectives

2.6.1 Secondary endpoint(s)

Secondary objective [1] is to describe the long-term efficacy of ligelizumab as measured by the tolerance of an allergen food protein during an open-label OFC at scheduled timepoints.

To satisfy the above secondary objectives the following endpoint will be taken into consideration:

Proportion of participants tolerating a single dose of \geq 600 mg of peanut protein without dose-limiting symptoms during an open label OFC at scheduled timepoints. This analysis will be based on FAS.

Secondary objective [2] is to assess the safety and tolerability of ligelizumab in all participants who administered study treatment at home by self-administration or parent/caregiver.

To satisfy the above secondary objectives the following endpoint will be taken into consideration:

Overall incidence rates of treatment emergent-AEs and SAEs will be analysis based on SAF-1.

Secondary objective [3] is to assess the long-term impact of ligelizumab on the health-related quality of life (HRQoL) of patients with food allergy.

To satisfy the above secondary objectives the following endpoint will be taken into consideration:

Summaries of total scores in the FAQLQ, FAIM, and SF-36v2 by age group and responder (participants and/or parent/caregiver) at scheduled timepoints.

This analysis will be based on FAS and latest available value at each visit will be used for summary.

Note: SF-36v2 completed by adults only.

For all efficacy endpoints, if missing Week 52-OFC assessments, Week 156-OFC assessments performed within 380 days (inclusive) after first extension dose date will be considered as Week 52-OFC assessments.

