2.6.2 Statistical method of analysis

The analysis of proportion of participants tolerating a single dose of \geq 600 mg of peanut protein without dose-limiting symptoms during an open label OFC at scheduled timepoints will be summarized with number and percentage of responders at Week 52, Week 104 and Week 156 by treatment group and overall.

To evaluate for all participants who administered study treatment at home by self-administration or parent/caregiver under the second secondary endpoints analysis for overall incidence of treatment-emergent adverse events (TEAEs) and serious adverse events (TESAEs) will be summarized as per Section 2.5.2.

Summaries for change from baseline in FAQLQ, SF-36v2 and FAIM domain and total scores will also be provided by age group and responder (participants and/or parent/caregiver) at scheduled timepoints (Refer Section 2.12).

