2.6.4 Handling of missing values not related to intercurrent event

Missing data will not be imputed.

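### For FAQLQ and FAIM the SAP keeps one value per annual visit, post-challenge by default and pre-challenge if that is missing, so change from Day 1 can mix two states with no visible count of either

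*SAP*

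**What the plan says.** Protocol 8.5.1 has respondents complete the questionnaires at home, twice around each annual challenge: they "should complete them 10 days before the OFC and 3 days after the OFC at Week 52, 104 and 156". Protocol Table 8-2 gives the two occasions separate columns. In that table every FAQLQ form (child, teenager, adult and parental) and every FAIM form appears in both columns. SF-36v2 and FAQL-PB appear at Day 1 and then only after the challenge.

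SAP 2.11 repeats the two-occasion schedule and then sets the analysis rule: "For analysis, will consider latest non-missing measurements". It adds the fallback: "If the 'post-' measurement is missing, then the non-missing 'pre-' measurement will be used". SAP 2.6.1 states the same rule for the secondary endpoint: "This analysis will be based on FAS and latest available value at each visit will be used for summary". The selected value feeds the change summaries of SAP 2.6.2: "Summaries for change from baseline in FAQLQ, SF-36v2 and FAIM domain and total scores will also be provided by age group and responder".

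For FAQLQ and FAIM, SAP 2.11 applies a threshold of 0.45 points to interpret both group-level and within-patient change. SAP 2.6.5 plans no sensitivity analyses.

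**The concern.** The protocol collects a before and an after score, and the SAP reports whichever is later. The two forms are completed in different circumstances. The challenge is open label, so by the post-OFC form the respondent knows the dose that was tolerated. For some participants the result also determines whether treatment is stopped, continued or restarted (Protocol 4.1.2). Several FAQLQ items ask about fear of a reaction, and FAIM asks how likely a severe reaction is (Protocol Appendix 9). A challenge result may plausibly move those answers.

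Two consequences follow:

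- The follow-up score is normally taken after a challenge, while the Day 1 score is not. The change from Day 1 can therefore include a response to the challenge itself as well as the state during the preceding year.
- Where post forms are missing, pre-challenge scores enter the same column. A reader of the table cannot tell how many of each it contains, and the proportions may differ between visits, age groups or dose groups.

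What is at stake is how the quality-of-life summaries are read, in particular against the 0.45 threshold.

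**Working it through.** The plan states no figure to reproduce. It gives no expected pre-to-post shift, standard deviation or completion rate for these instruments. The check is a comparison of the rules, followed by algebra in symbols.

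**Step 1: which instruments have a pair to collapse (Protocol Table 8-2).**

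| Instrument | Day 1 | Before OFC | After OFC |
|---|---|---|---|
| FAQLQ, all forms including parental | yes | yes | yes |
| FAIM | yes | yes | yes |
| SF-36v2 (adults) | yes | no | yes |
| FAQL-PB (parents) | yes | no | yes |

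The selection rule matters only for FAQLQ and FAIM. For the other two, every annual value is post-OFC by design. SAP Table 2-2 is damaged in the text available and is not relied on.

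**Step 2: the state of the baseline form.** Protocol 1.3 requires PROs to be completed before any other assessment at a visit. Footnote 7 to Table 1-4 limits the Day 1 OFC to participants who were maximum responders at the end of core-study treatment. So the Day 1 form precedes any Day 1 challenge, and most of the schedule has no Day 1 challenge at all. The SAP's formal definition of baseline is not visible. Day 1 is taken as baseline because it is the only pre-treatment PRO occasion in Table 8-2.

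**Step 3: what the reported mean contains.** Suppose every participant has a pre-OFC form. Let

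- A = mean change from Day 1 to the pre-OFC form, all participants;
- f = share whose post-OFC form is missing, so that the pre-OFC value is used;
- d = mean post-minus-pre difference in those with both forms.

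Then reported mean change = A + (1 − f) × d.

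- f = 0: A + d. Nothing is mixed; every value is post-OFC.
- f = 0.30: A + 0.7d.
- f = 0.50: A + 0.5d.

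The contrast between a post-challenge score and the Day 1 form is thus greatest when no post form is missing. Mixing arises only when f is above 0.

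**Step 4: differing completion.** If f is 0.10 at one visit or in one dose group and 0.30 at another, the challenge terms are 0.9d and 0.7d. They differ by 0.2d with no difference in A or d.

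**Step 5: direction.** Suppose, for illustration, that scores move by −s after a passed challenge and +s after a failed one, with pass rate p. Then d = (1 − 2p) × s:

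- p = 0.30 gives +0.4s;
- p = 0.50 gives 0;
- p = 0.70 gives −0.4s.

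The sign depends on the pass rate, which the documents do not give. All values of f, p and s are assumptions.

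**The case against.** The strongest reply is that this is an ordinary visit-level selection rule, stated consistently in two sections of a descriptive plan for a trial that was stopped early. The protocol promised summaries at scheduled time points and left the detail to the SAP (Protocol 9.4.3). It also made post-OFC the only annual occasion for SF-36v2 and FAQL-PB, so a post-OFC default follows part of the design. There is no placebo arm, so neither choice of form would allow change to be attributed causally to treatment. All of that stands, and it limits the consequence.

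Nor is the pre-OFC form a perfect match for Day 1. It is completed shortly before a procedure for which Protocol 2.3 acknowledges emotional distress. By Weeks 104 and 156 the participant also knows earlier results. It can be called unaffected only by that visit's result.

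Stronger readings that a reader might infer, and why the documents do not support them:

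- *That the challenge effect alone could reach the 0.45 threshold.* No post-minus-pre shift is given anywhere. Setting d to 0.45 and finding that it reaches 0.45 is circular. Step 3 also shows that this term is largest when the fallback is never used.
- *That the fallback breaks the SAP's own missing-data rule, "Missing data will not be imputed".* The rule chooses between two values that were actually observed around the same visit. That is selection rather than imputation.
- *That participants who reacted skip the post form more often, so the bias is selective.* Nothing in the documents bears on this.
- *That separate tables are definitely absent.* SAP 2.6.2 sends the reader to Section 2.12, which is not visible. The general definitions and exploratory analyses are also withheld.

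**Conclusion.** The point holds for FAQLQ (including the parental form) and FAIM only. On the visible text, the reported change from Day 1 is a mainly post-challenge score minus a score taken before any Day 1 assessment. It is diluted by pre-challenge scores to an extent set by post-form completion, and that extent is not reported. The challenge contribution is (1 − f) × d, with neither term available, so neither size nor direction can be stated. No test, error rate or sample size is affected. This is a worthwhile, inexpensive gain in interpretability and does not amount to a demonstrated bias. It rests on two assumptions: that Day 1 is the analysis baseline, and that the withheld SAP sections do not already provide separate summaries.

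**What to change.** In SAP 2.6.1, 2.6.2 and 2.11, for FAQLQ and FAIM:

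- summarise pre-OFC and post-OFC scores, and the change of each from Day 1, as separate time points at Weeks 52, 104 and 156;
- give the n for each column and drop the substitution of one form for the other;
- identify the pre-OFC change as the comparison not affected by knowing that visit's challenge result.

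Label the annual SF-36v2 and FAQL-PB scores as post-OFC measures, following Protocol Table 8-2. If the withheld sections already contain such tables, a cross-reference to them from 2.6.2 and 2.11 is enough.

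The data are already scheduled for collection. The cost is extra columns in existing tables and a smaller n in each column than the combined value would have.

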10.9.4 FAIM-TF: Food Allergy Independent Measure Teenager Form

ood	allergy. Choo	r questions are ab ose one of the ans putting an 'x' in the	swers provided.	This is followed	by two more q							
	0 never chance)	1 very small chance	2 small chance	3 fair chance	4 great chance		5 grea			6 alwa		e)
Hov	great do	you think the o	chance is tha	t you		0	1	2	3	4	5	6
1.	will accide	entally eat some	thing to which	you are allerg	gic?							
2.		a severe reactio are allergic?	n if you accide	entally eat son	nething to							
3.	will die if y	ou accidentally	eat something	to which you	are allergic?							
4.		ffectively deal w lly eat somethin										
		many product		void 6	. How grea					ur fo	od	
	Па	lmost none			neglig	ibly sma	III					
	□ v	ery few			☐ very s	mall						
	Па	few			small							
	☐ s	ome			☐ moder	ate						
	_	nany			great							
	□ v	ery many			☐ very g	reat						
	□a	lmost all			extren	nely grea	at					

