Bec 27 28 29	worried about his/her future (opportunities, relationships) Many people do not understand the serious nature of food allergy Concerned by poor labelling on food products	0	1	2	3	4	5 6

Food Allergy Independent Measure (FAIM Items are answered on a 0-6 or 1-7 point response	scale as preferred,
with a greater score indicating a higher level of pe Question 4 must be reverse scored before a Total s	
How great do you think is the chance the	hat your child 0 1 2 3 4 5
1 will accidentally eat something to which he/sl	he is allergic?
will have a severe reaction if he/she accidenta which he/she is allergic?	ally eat something to
3 Will die if he/she eats something to which he/	she is allergic?
4 will effectively manage a reaction or will rece others if a reaction occurs?	eive sufficient help from
5. How many foods must your child avoid	6. How much has your child's food allergy
5. How many foods must your child avoid because of food allergy?	6. How much has your child's food allergy limited the type of activities your child can take part in?
because of food allergy?	limited the type of activities your child can take part in?
because of food allergy? almost none very few	limited the type of activities your child can take part in? so little he/she doesn't actually notice it very little
because of food allergy? almost none very few a few	limited the type of activities your child can take part in? so little he/she doesn't actually notice it very little little
because of food allergy? almost none very few a few some	limited the type of activities your child can take part in? so little he/she doesn't actually notice it very little little moderately
because of food allergy? almost none very few a few some many	limited the type of activities your child can take part in? so little he/she doesn't actually notice it very little little moderately a good deal
because of food allergy? almost none very few a few some	limited the type of activities your child can take part in? so little he/she doesn't actually notice it very little little moderately

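### SAP 2.11 orders FAIM questions 4 and 5 reverse coded, but the printed form reverses only question 4, and question 5 already rises with severity

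*SAP*

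**What the plan says.** The scoring part of SAP 2.11 recodes FAIM answers from 0–6 to 1–7, averages the completed items, and withholds the total if fewer than 80% of items are complete. A greater score is to mean higher perceived risk. It then adds: "Questions 4 and 5 (effectively managing a reaction, receiving sufficient help from others) must be reverse coded". Earlier in the same section, "The total score for the FAIM ranges from 1 to 7", where 1 is limited and 7 is the greatest perceived severity.

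The parent FAIM, printed within protocol 10.9.7, carries its own scoring note: "Question 4 must be reverse scored before a Total s" (the line is cut off in the copy reviewed). It names no other item. Question 4 on that form begins "will effectively manage a reaction or will rece" and goes on to receiving enough help from other people. Question 5 asks "How many foods must your child avoid because of food allergy".

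FAIM enters the third secondary endpoint twice. SAP 2.6.1 calls for "Summaries of total scores in the FAQLQ, FAIM, and SF-36v2 by age group and responder", and SAP 2.6.2 adds "Summaries for change from baseline in FAQLQ, SF-36v2 and FAIM domain and total scores". SAP 2.11 applies a 0.45-point threshold to group-level differences, group-level changes and within-patient changes.

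**The concern.** The SAP's item numbers do not match the form. Its brackets describe two things, managing a reaction and getting help, as if they were questions 4 and 5. On the parent form they are two halves of question 4. The item actually numbered 5 is a count of foods avoided and needs no reversal.

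The instruction can therefore be read in two ways that give different scores. Item numbers are what derivation code normally uses, so the wrong reading is a realistic one. It would put one of six items into the average with the wrong sign. A participant who has to avoid fewer foods would then look worse on that item, and one who has to avoid more would look better. Both the reported FAIM levels and the judgement of whether a change reaches 0.45 could be affected.

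**Working it through.** **Step 1. Compare the forms item by item.**

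| Form (protocol) | Question 4 | Question 5 | Scoring note |
|---|---|---|---|
| Parent (10.9.7) | managing a reaction or receiving help | foods avoided; legible answers rise from *almost none* to *many* | reverse question 4 |
| Teenager (10.9.4) | fragment: "ffectively deal w" | products avoided; *almost none* to *almost all* | none visible |
| Adult (10.9.6) | same fragment as the teenager form | products avoided; *almost none* to *almost all* | none visible |
| Child (10.9.2) | text lost in the copy reviewed | partly lost; answers start at *almost none* and rise | none visible |

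On no legible form is question 5 about receiving help. Wherever its answers can be read, they rise with severity. Question 4 is positively worded on the three forms where it can be read, so it does need reversing.

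**Step 2. Test each rule against the SAP's own 1-to-7 scale.** There are six items coded 1 to 7; a reversed item becomes 8 minus its code; the total is the mean. Before any reversal, the most severe pattern is 7 on every item except question 4, which is 1. The least severe pattern is the opposite.

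- Reverse question 4 only: least severe 6 × 1 / 6 = 1.0; most severe 6 × 7 / 6 = 7.0. This reproduces the stated ends.
- Reverse questions 4 and 5: least severe (5 × 1 + 7)/6 = 2.0; most severe (5 × 7 + 1)/6 = 6.0. This does not.

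**Step 3. Displacement of a total score.** With question 5 coded x, flipping it replaces x by 8 − x. The complete total moves by ((8 − x) − x)/6 = (8 − 2x)/6. If one other item is missing, 5/6 = 83% are complete, the total is still calculated, and the divisor is 5.

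| x | 1 | 2 | 3 | 4 | 5 | 6 | 7 |
|---|---|---|---|---|---|---|---|
| Six items | +1.00 | +0.67 | +0.33 | 0 | −0.33 | −0.67 | −1.00 |
| Five items, question 5 answered | +1.20 | +0.80 | +0.40 | 0 | −0.40 | −0.80 | −1.20 |

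If question 5 is itself the missing item, the displacement is 0. As a yardstick only, the six-item shift is larger than 0.45 at x = 1, 2, 6 and 7.

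**Step 4. Displacement of change from baseline.** Let d be the change in question 5, with all six items answered at both visits. Its correct contribution is d/6 and its flipped contribution is −d/6, so the error is −2d/6 = −d/3. Its size is 0.33 for one category, 0.67 for two, and 0 if question 5 is unchanged. For the error alone to exceed 0.45, question 5 must change by more than 0.45 × 3 = 1.35 categories: two or more in an individual, or more than 1.35 on average in a group.

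**Step 5. Illustration.** Suppose questions 1, 2 and 5 each improve by one category. The correct change is −3/6 = −0.50, beyond 0.45. With question 5 flipped it is (−1 − 1 + 1)/6 = −0.17, short of it. If question 5 instead worsens by one category, the correct change is −0.17 and the scored change is −0.50.

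**The case against.** The strongest reply is that the error is conditional and its consequence limited. The bracketed words point to question 4, so a careful programmer would score correctly. Neither the derivation code nor the annotated CRF listed in the SAP references is available, and the CRF might number the items differently. The study was terminated early, the analyses are purely descriptive (SAP 1.2), and FAIM is one of three instruments in one secondary endpoint.

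The evidence also has limits. The scoring note is printed on the parent form only, the teenager and adult wording survives as fragments, and the child form's question 4 is lost. The 0.45 threshold is meant for differences and changes, not score levels, and a level shift from a stable question 5 cancels in change from baseline. Inclusion criterion 4 (protocol 5.1) requires continued avoidance, so question 5 may often be stable.

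Much of this stands. It limits the likely size in change scores, and it means that the level shifts in Step 3 are not threshold breaches in themselves. It does not remove the mismatch. Nothing in either document reconciles the SAP's numbering with the printed forms; if the CRF numbers items differently, the SAP needs to say so. Levels are reported in their own right under SAP 2.6.1, and those do not benefit from cancellation. A descriptive endpoint still needs correctly scored values.

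**Conclusion.** The concern holds. The SAP's reverse-coding instruction is wrong by item number, and it should be corrected before FAIM results are produced. Reversing question 4 alone agrees with the printed scoring note and restores the SAP's own 1-to-7 scale.

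The size applies only if the item numbers are followed. Score levels are then displaced unless question 5 is at its midpoint or missing. Changes from baseline are displaced only in participants whose question 5 answer changes: improvement is understated where that item improves and overstated where it worsens. How many scores would be affected cannot be determined from the documents. The conclusion is firmest for the parent form, well supported for the teenager and adult forms, and still to be confirmed for the child form. The primary endpoint is not touched.

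**What to change.** Replace the sentence in SAP 2.11 with one that names a single item, for example: *Question 4 (dealing effectively with a reaction; on the parent form, also receiving help) is reverse coded. Question 5 (number of foods or products avoided) is scored as answered.*

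Before finalising it, confirm the question 4 wording and the item numbering on the complete child, teenager and adult forms and in the annotated CRF. Then check the FAIM derivation code against the corrected rule: the least and most severe patterns should return exactly 1 and 7. Do this before any FAIM total or change is summarised or read against 0.45.

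The cost is one SAP sentence and a check of one line of code. No new data are needed, and there is no downside.
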